### **9.2.5 Voiding Assessment(s)**

Prior to bladder voiding, the research staff will task the patient to locate the Connected Catheter end and assess if any migration has occurred. Next, the subject is to perform bladder voiding using the Controller, and the PVR Volume is then measured and recorded. The subject will remain in the vicinity of Study clinic premises for additional bladder filling and voiding cycles, to be conducted in the same manner without repeating the positioning and sizing assessment. A total of 3 voiding cycles will be performed during the initial insertion visit and twice during each Test Phase visit.

### **9.2.6 Expectation Management for New Users – Anti-Cholinergic and other medications**

Subjects transitioning from other methods of bladder management should expect a short period of time in which their body adapts to the Connected Catheter. This may include various symptoms including discomfort and pain. The Clinical Research staff should educate and inform the subject about this possibility and help to manage their expectations as they become accustomed to the device.

Subjects with higher levels of sensation may have a more difficult time adapting to the Connected Catheter. For all subjects, the clinician should review subject's history for any anti-cholinergic or other medications (e.g. Myrbetriq) that the subject has been treated with previously and consider starting an appropriate course of medication 1-2 weeks prior to the initial insertion and continue at least 1-2 weeks after the Connected Catheter has been inserted. This medication may help to alleviate any discomfort as the subject transitions to the Connected Catheter. Additionally, it may

help indwelling catheter users to increase bladder capacity as they begin using the Connected Catheter.

There are no other medical devices or medications that will be utilized during this study.

### **9.2.7 Clinic Assessment Completion and Subject Discharge**

Prior to discharge, the subject will complete the Connected Catheter User Experience Survey. If the Connected Catheter fulfills the objective performance criteria for all areas of essential performance (insertion, voiding and anchoring) then the subject will leave with their current Connected Catheter inserted, be scheduled for the next office appointment (at Day  $7 \pm 1$ ), and will be discharged from the Study Site for the Device Tolerability Screening Phase.

## **9.3 Device Tolerability Screening**

During the Device Tolerability Screening, subjects will use the Connected Catheter to manage their chronic Urinary Retention. The duration of Tolerability Screening will be up to 7 days after the patient has had the first device inserted. The purpose of this screening is to ensure that the subjects can both tolerate the device and learn how to operate it properly. Any subject that experiences significant discomfort or cannot demonstrate proficiency in the operation of the device (or does not have a caretaker) will not proceed to the test phase of the study. Patients that are able to successfully use the device for up to 7 days and wish to continue the study will progress to the test phase. The data collection during the Device Tolerability Screening is identical to the data during the Test Phase. The subjects will be trained to manage his bladder using the Connected Catheter via the Controller on an intermittent voiding strategy. Instructions for Use (IFU) will be provided to the subject regarding how to properly use the Connected Catheter. The same assessments used in the Test Phase will be done at the end of the Device Tolerability Screening phase.

## **9.4 Test Phase**

The Test phase will require three (3) Exchange Appointments and a final Removal Appointment. Each appointment will assess PVR, voided volume, quality-of-life (QOL), and urinary tract injury, adverse events, medication, and other study assessment. Additionally, the subjects will be asked to fill out a User Experience Survey and Safety and Performance Survey and the device will be evaluated for fit, migration, placement, and removal.

At each exchange visit, the clinic research staff will follow these procedures:

1. Patient Arrival – Vital Signs and other measurements
2. Bladder Volume – Measurement using Ultrasound to ensure at least 200 mL of urine
3. Patient empties bladder – PVR volume measurement using Ultrasound
4. Patient removes Connected Catheter
5. Patient waits for bladder to fill – additional surveys completed
6. Patient inserts new Connected Catheter and bladder emptied – PVR volume measured
7. Patient Departure

For the final device removal visit the clinic research staff will follow these procedures:

1. Patient Arrival – Vital Signs and other measurements
2. Bladder Volume – Measurement using Ultrasound to ensure at least 200 mL of urine
3. Patient empties bladder – PVR volume measurement using Ultrasound
4. Patient removes Connected Catheter
5. Patient completes all surveys
6. Patient departure

Once the patient completes the final device removal visit the patient will enter the follow-up phase.

## 9.5 Follow-Up Phase

During the Follow-Up Period, subjects will use their previous method of bladder management for 2 weeks following their Final Device Removal Appointment. During this period, the patient will receive a phone call each week to screen for the occurrence and/or persistence of lower urinary tract symptoms and other issues that may be related to Connected Catheter usage, using the Follow-Up Phone Call Survey. If any issues are identified that may require clinician intervention, then the research staff will schedule the patient for a clinic appointment with the appropriate provider. At this appointment, the clinician will screen for any complications and attempt to document any symptoms that may be indicative of a complication related to Connected Catheter use.

## 9.6 Unscheduled Follow-up Visits

If subjects are seen for unscheduled/interim visits because of an AE, appropriate Case Report Form(s), including the AE CRF, will be completed, if applicable. At the investigator's discretion, some of the evaluations and tests may be repeated if indicated. Sponsor requests that if any additional tests or procedures listed within this clinical investigation protocol are performed during an unscheduled visit the investigator provide the results on the Unscheduled Visit CRF.

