As part of their training to use the Gen 2 Connected Catheter System, subjects will be trained to remove the Connected Catheter using the IR Tool and will be provided with an IR Tool to keep available at all times throughout the Test Phase, in the event that the Connected Catheter must be removed at any time.

During the Test Phase of the Study, subjects will maintain the phone number of the clinic should any adverse events arise. Staff will provide any necessary medical or device-related guidance.

All Study Investigators will be thoroughly trained in this clinical investigation protocol, including the Gen 2 Connected Catheter System and Accessories Clinician Instructions for Use (IFU) and procedural elements of the study.

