### **8.5 Primary Endpoints**

#### **8.5.1 Primary Efficacy**

During each follow-up, and during the initial device insertion and evaluation, the Post-Void Residual (PVR) urine volume will be measured via ultrasound.

A subject will be considered a responder to the device if at least 80% of the subject's available PVR values are:

- a. Less than 50 mL OR
- b. Equal or less than baseline PVR with the standard urinary management system

If a subject drops out before the conclusion of the study after passing the Device Tolerability Screening, their PVR data will still be included in the primary analysis.

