**Table 9-2: Schedule of Visits**

	Eligibility Screening	Device Tolerability Screening	Test Phase	Follow-Up	Unscheduled
Compliance window		<math>7 \pm 1</math> days	<math>7 \pm 1</math> days	<math>7 \pm 1</math> days	
Basic Vital Measurements	✓	✓	✓		✓
Physical Examination	✓				
Urinary Tract Visual Examination	✓				

	Eligibility Screening	Device Tolerability Screening	Test Phase	Follow-Up	Unscheduled
(cystoscopic, if necessary)					
Catheter Assessment Tool (CAT) Evaluation	✓				
Medical History	✓				
UTI Assessment including Urinalysis	✓	✓	✓		
PVR Measurement	✓	✓	✓		
Voiding Volume Measurement	✓	✓	✓		✓
SCI-QOL Bladder Management Survey	✓	✓	✓		
Current Catheter Experience Survey	✓				
Medication(s) used	✓	✓	✓		✓
Connected Catheter User Experience Survey		✓	✓		
Connected Catheter Safety and Performance Survey		✓	✓		
USQNB-IC Survey	✓	✓	✓		
Connected Catheter Weekly Assessment Includes: 
 
• Device Insertion Assessment
 
• Device Sizing
 
		✓	✓		

	Eligibility Screening	Device Tolerability Screening	Test Phase	Follow-Up	Unscheduled
and Positioning					

 
• Catheter Sealing
 
• PVR Measurement
 
• Voided Volume
 
• Catheter Migration
 
• Urethral Injury Assessment
 
• Device Removal Assessment
 
• QOL Survey
 
					
Follow-Up Phone Screening for Potential AE				✓	
Adverse event(s) review		✓	✓	✓	✓
There are weekly appointments during the Test Phase and weekly phone calls during the Follow-Up Phase					

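### PVR and the device assessment are discretionary at unscheduled visits and no rule scores a catheter removed or replaced early, so a between-visit failure may leave no failing value

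*Combined protocol and SAP*

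**What the plan says.** In Table 9-2 the Unscheduled column ticks vital signs, "Voiding Volume Measurement", medications and adverse event review. The row "PVR Measurement" is ticked for the two screening stages and the Test Phase, but not for unscheduled visits. The row beginning "Connected Catheter Weekly Assessment Includes" covers insertion, sizing, sealing, migration, urethral injury and removal. It is ticked only for Device Tolerability Screening and the Test Phase, as is the Safety and Performance Survey.

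Section 9.6 opens with "If subjects are seen for unscheduled/interim visits because of an AE", so a device failure without an adverse event is not addressed. It continues: "At the investigator's discretion, some of the evaluations and tests may be repeated if indicated". If protocol tests are done, the sponsor asks that "the investigator provide the results on the Unscheduled Visit CRF".

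Three other places bear on this:

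- Section 8.5.1 has PVR measured at every follow-up and at the initial insertion. Its rule reads: "A subject will be considered a responder to the device if at least 80% of the subject's available PVR values are" within the stated limits. Section 10.1 repeats the restriction to available values.
- Section 9.2.2 gives the Safety and Performance Survey at every appointment where the device is replaced.
- Section 7.2 provides each subject with an IR Tool "in the event that the Connected Catheter must be removed at any time". Removal between visits is therefore foreseen.

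**The concern.** Take a man whose catheter stops emptying, leaks or migrates on day 3 and who stays in the study. Either he removes it at home, or it is replaced at an unscheduled visit. In neither case does the schedule require a PVR on the failed catheter. At the next weekly visit there is either no worn catheter to scan or a replacement worn for only part of the week. Since the responder rule uses only available values, the failed catheter is then omitted or stands behind a passing value.

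The readings most likely to be lost are those lost because the device failed, so the error runs in the device's favour. The withdrawal rules in 9.7 do not help, because this man continues. At stake are the primary responder rate and, to a lesser degree, the anchoring and sealing results in secondary endpoints 1 and 2.

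**Working it through.** **The plan's own figure.** Section 8.8 takes 24 men into tolerability screening and assumes 33% dropout: 24 × (1 − 0.33) = 16.08, which gives the stated minimum of 16 evaluable. No power is stated.

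**Readings per completer.** Section 9.2.5 gives three voiding cycles at insertion. Section 9.3 says the end of tolerability screening uses the Test Phase assessments, taken here as two PVR values (an inference). Section 9.4 gives two PVR values at each of three exchange visits and one at final removal.

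- All visits: 3 + 2 + 3 × 2 + 1 = 12. Five of these are on a worn catheter (1 + 3 + 1).
- Test Phase only: 3 × 2 + 1 = 7. Four of these are on a worn catheter.

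Section 9.2.5 can also be read as two cycles at the removal visit, which gives 13 or 8.

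**Effect on one man's status (80% needed).** All other readings are taken to pass.

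| Failing worn readings | All recorded | Catheters removed early, readings lost | Catheters replaced early, replacement passes |
|---|---|---|---|
| 1 of 12 | 11/12 = 91.7% | 11/11 | 12/12 |
| 2 of 12 | 10/12 = 83.3% | 10/10 | 12/12 |
| 3 of 12 | 9/12 = 75.0%, non-responder | 9/9 = 100% | 12/12 = 100% |
| 2 of 7 | 5/7 = 71.4%, non-responder | 5/5 = 100% | 7/7 = 100% |

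The thresholds are the same with 13 or 8 readings: 10/13 = 76.9% and 6/8 = 75.0%. Fewer losses matter if other failures are already on record. With three failures of which only one is lost, the score is 9/11 = 81.8% in place of 9/12 = 75.0%.

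**Adding or substituting.** If failing unscheduled values are added to 12 scheduled passes, three give 12/15 = 80.0%, still a responder; it takes four (12/16 = 75.0%). The 75.0% for three failures holds only if the failed reading occupies its scheduled slot.

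**Effect on the test.** Section 10.3 specifies an exact binomial test, one-sided 0.05, null rate 0.60. At n = 16:

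- P(X ≥ 14 | 0.60) = 0.0183, so 14 responders succeed.
- P(X ≥ 13 | 0.60) = 0.0651, so 13 fail.
- P(X ≥ 14 | 0.90) = 0.789, the power at the rate that 10.2 expects to be exceeded.

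One reclassified man changes the result when the count stands at 14.

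**The case against.** A reader might infer that a between-visit failure always leaves no failing value. The documents do not say that. Section 9.6 permits a PVR at the visit and asks for the result, the responder rule does not exclude unscheduled values, and 8.5.1 can be read as already requiring PVR at any follow-up. What stands is that capture is discretionary and use of the value undefined.

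A reader might also infer that such failures vanish from secondary endpoints 1, 2 and 5. That too goes beyond the text. Section 8.6 does not tie those endpoints to the Weekly Assessment alone. Retention, incontinence and lower urinary tract injury are anticipated adverse events in 11.9, and adverse events are reviewed at unscheduled visits. Urinary tract injury is assessed again at each Test Phase appointment (9.4). Section 9.2.2 would have the survey done at a replacement appointment, and 11.6 and Table 14-1 make some deficiencies and malfunctions reportable. Injury in particular has a direct route into the data. But no rule carries these records into the responder rate or into a count of failed catheters.

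The scenario is narrow. With 12 readings, one or two lost failures alone change nothing. The first catheter must be used successfully for the man to progress, so three failures would in practice mean three of the four Test Phase catheters. This limits the size but does not remove the gap.

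Finally, 10.3 plans tipping point analyses for missing data. These can address a reading that is absent. They cannot see a replaced catheter, because a value is present. That value is a genuine reading on the replacement, but it says nothing about the catheter that failed.

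**Conclusion.** The point holds as a gap in data capture and scoring. Table 9-2, 9.6, 8.5.1 and 9.2.2 disagree on what is assessed at an unscheduled visit and must be reconciled. No rule says whether unscheduled PVR values count or how a catheter removed or replaced early is scored. The direction favours the device.

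The size is unknown, since the documents give no rate of between-visit failure. A reader might conclude that the responder rate will be overstated or that one or two men will decide the test; the figures show sensitivity only. They rest on about 12 readings per man (7 if only the Test Phase counts), 16 evaluable men, and repeated failure in the same man unless he already has failures recorded. The change is worth making because it is cheap and can be settled before data are seen.

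**What to change.** 1. In Table 9-2, tick PVR Measurement under Unscheduled when a Connected Catheter is in place, taken before any removal and under the same 200 mL pre-void condition as other visits. Tick the Weekly Assessment and the Safety and Performance Survey when a catheter has been removed, expelled or replaced since the last visit. Align 9.6, 8.5.1 and 9.2.2 with this.
2. In 8.5.1 and 10.1, state that these PVR values count as available. State also that a worn-catheter reading lost because that catheter was removed or replaced for failure to empty is scored as not met. This must include removal at home reported at the next visit, which a schedule tick alone would miss. Say that the not-met value takes the scheduled slot, and that one failed catheter contributes one such value, so that an unscheduled failing PVR on it is not counted twice.
3. In 8.6, count each catheter removed, expelled or replaced early for migration or leakage as a failure of anchoring or sealing under secondary endpoints 1 and 2. Keep these out of the PVR endpoint, which should reflect emptying only.

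None of this alters when a catheter is removed or replaced; that remains with the investigators. The cost is a few extra bladder scans with equipment already used at scheduled visits, some added text, and possibly slightly less favourable responder and device-success rates.

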**Table 9-2: Schedule of Visits**

	Eligibility Screening	Device Tolerability Screening	Test Phase	Follow-Up	Unscheduled
Compliance window		<math>7 \pm 1</math> days	<math>7 \pm 1</math> days	<math>7 \pm 1</math> days	
Basic Vital Measurements	✓	✓	✓		✓
Physical Examination	✓				
Urinary Tract Visual Examination	✓				

	Eligibility Screening	Device Tolerability Screening	Test Phase	Follow-Up	Unscheduled
(cystoscopic, if necessary)					
Catheter Assessment Tool (CAT) Evaluation	✓				
Medical History	✓				
UTI Assessment including Urinalysis	✓	✓	✓		
PVR Measurement	✓	✓	✓		
Voiding Volume Measurement	✓	✓	✓		✓
SCI-QOL Bladder Management Survey	✓	✓	✓		
Current Catheter Experience Survey	✓				
Medication(s) used	✓	✓	✓		✓
Connected Catheter User Experience Survey		✓	✓		
Connected Catheter Safety and Performance Survey		✓	✓		
USQNB-IC Survey	✓	✓	✓		
Connected Catheter Weekly Assessment Includes: 
 
• Device Insertion Assessment
 
• Device Sizing
 
		✓	✓		

	Eligibility Screening	Device Tolerability Screening	Test Phase	Follow-Up	Unscheduled
and Positioning					

 
• Catheter Sealing
 
• PVR Measurement
 
• Voided Volume
 
• Catheter Migration
 
• Urethral Injury Assessment
 
• Device Removal Assessment
 
• QOL Survey
 
					
Follow-Up Phone Screening for Potential AE				✓	
Adverse event(s) review		✓	✓	✓	✓
There are weekly appointments during the Test Phase and weekly phone calls during the Follow-Up Phase					

## 9.7 Subject Loss to Follow-Up or Withdrawal

### 9.7.1 Subject Discontinuation/Withdrawal Criteria

#### 9.7.1.1 Voluntary Withdrawal

Participation in this clinical investigation is entirely voluntary. Further, once the subject has been enrolled in the study, he may withdraw his consent to participate in the study at any time, without further obligation or penalty. If a subject officially withdraws from the study, the investigator must ensure that the reason for the withdrawal is documented.

If the subject had an AE, the subject should be followed until the resolution of the AE, if possible. Data from these subjects will be included in the analysis up to the point of each subject's withdrawal.

### **9.7.1.2 Involuntary Withdrawal**

Likewise, there may be a reason identified by the Investigator that deems the subject no longer suitable for the study, in which case the subject may be withdrawn by an Investigator. In either case, the Investigator should contact the Sponsor to discuss the circumstances for discontinuation/withdrawal. Reasons for discontinuation or withdrawal may include, but are not limited to the following:

1. Subject is uncooperative with compliance of required study tests, medical management and/or Study procedures
2. Investigator determines that subject has developed a condition for which continued participation in the study is potentially harmful to the subject
3. Subject withdraws his consent
4. Subject is lost to follow-up
5. Subject has a significant protocol violation
6. Subject is found to have been incorrectly enrolled in the study
7. Sponsor terminates the study

### **9.7.1.3 Data Withdrawal Due to Exclusion Criteria**

A subject's data may be excluded from the analysis if the subject is later found not to meet one or more major exclusion criteria. However, these subjects will continue to be followed per the requirements of their particular arm unless instructed otherwise by the IRB/EC.

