## 8 CLINICAL STUDY DESIGN

The FREEDOM Study is a prospective, open, single-arm, non-significant risk (NSR) study to be performed in the United States with consecutive enrollment to evaluate the safety and efficacy of the Connected Catheter System in treating subjects with chronic Urinary Retention. All patients

that sign an informed consent form are considered to be part of the intended-to-treat (ITT) population.

The study will be broken up into 4 phases – Eligibility screening, Device Tolerability screening, Connected Catheter use, and Follow-Up. Figure 8-1 shows an overview of the study with the estimated sample size enrolled and treated.

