### **8.8 Number of Sites and Sample Size**

Up to 4 sites in the United States are planned for this study.

The number of subjects to be enrolled in the study (ITT) as defined by EN ISO 14155; is 36 subjects. Of these, it is expected only 24 of the subjects will be found to meet the basic eligibility criteria to be tested for device tolerability screening.

Assuming a 33% dropout after the device tolerability screening, the final number of evaluable subjects required is a minimum of 16 subjects (See 10.1).

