### 9.2.1 Insertion and Initial Voiding Assessment

The Insertion Procedure is to begin with the insertion of the Connected Catheter using the IR Tool, according to device training procedures and Instructions for Use (IFU). The initial insertion will be performed by a trained clinician. Once the Connected Catheter has been placed, a urine sample will be collected and sent out for urinalysis and urine culture. Note that the subject must have at least 200 mL of urine in the bladder, as measured by ultrasound, prior to voiding and sample collection. After the bladder is emptied, a member of the research team (physician, nurse, etc.) will measure PVR volume using an ultrasound bladder scanner and record this reading.

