### 10.2 Sample Size Justification

Based upon historical data and experience with the device, the estimate of R is expected to exceed 90% in this study. Limited descriptive statistical methods will be utilized to analyze data collected from this protocol. Although there will be limited power achieved with the number of patients completing this study, this data will provide a foundation for further clinical research with additional statistical rigor.

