## 14.2 Subject Enrollment Process

All study candidates, after pre-screening, must appropriately consent to participate in the study, as administrated by qualified study site personnel using an IRB and Sponsor-approved informed consent form (ICF) prior to beginning any aspect of the study procedure or tests that are not standard of care for the site. Investigational sites will be required to document the consent process within each enrolled subject's medical record. Administering the questionnaires can be done prior to signing the ICF.

Only subjects who meet the inclusion/exclusion criteria, who signed the study enrollment informed consent will be considered enrolled in the study.

Timely communication by each site is critical to avoid over enrolling when the enrollment is close to the end of each phase.

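### Section 9.7.1.3 lets a treated man's data be dropped on an unspecified major exclusion criterion, with nothing requiring the choice to be made without sight of PVR

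*Combined protocol and SAP*

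**What the plan says.** Section 9.7.1.3 provides: "A subject's data may be excluded from the analysis if the subject is later found not to meet one or more major exclusion criteria". It then adds that "these subjects will continue to be followed per the requirements of their particular arm", so the rule reaches men who are still being followed.

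The primary efficacy test (section 10.3) is a one-sided exact binomial test of a responder rate of 0.60 or less, at the 0.05 level, on the mITT population. That term is not defined in section 10.3 or elsewhere, and the abbreviation list gives only ITT. The nearest thing to a definition is in section 8.5.1: for a man who drops out after passing Device Tolerability Screening, "their PVR data will still be included in the primary analysis".

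Two other sections bear on a man found ineligible. Section 9.7.1.2 lists incorrect enrollment as a reason for withdrawal, and section 9.7.1.5 keeps a withdrawn man's data up to the time he leaves.

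Section 8 describes an open, single-arm study. At the first insertion a member of the research team "will measure PVR volume using an ultrasound bladder scanner and record this reading", and section 9.4 has PVR measured at every exchange visit and at the final removal visit. On size, section 8.8 expects 24 men to enter tolerability screening and says "the final number of evaluable subjects required is a minimum of 16 subjects".

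**The concern.** The rule permits removal without requiring it. Neither eligibility list (synopsis and section 8.7.2) ranks its criteria, so *major* has no content. The plan does not say who decides, when, or on what information. By the time a breach comes to light, the man's PVR values may already be known at the site.

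Nothing else settles the matter. Section 8.5.1 deals with dropouts and not with ineligibility found later. Under section 9.7.1.5, a man withdrawn as incorrectly enrolled keeps his data in the analysis. Under section 9.7.1.3, a man with the same fault who continues may lose his. Two analysts could both follow this document and report different denominators for the primary test.

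At stake is whether the 5% level can be relied on. The test is run on a small set, so at some sample sizes removing one non-responder changes the result.

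**Working it through.** **Inputs.** Null rate 0.60, one-sided 0.05, exact binomial (sections 10.1 and 10.3). 24 men entering tolerability screening, 33% dropout, minimum 16 evaluable (section 8.8). The plan's count reproduces: 24 × (1 − 0.33) = 16.08. Because dropouts after screening stay in and mITT is undefined, the tested n could lie anywhere from 16 to 24.

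**Can a removal reverse the test?** The p-value for x responders among n is P(X ≥ x), with X ~ Bin(n, 0.60). For each n, take the largest count that just fails, remove one non-responder, and test again.

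| n | responders needed | type I error, no removal | near miss, p | after one removal, p |
|---|---|---|---|---|
| 16 | 14 | 0.018 | 13/16, 0.065 | 13/15, 0.027 (below the minimum) |
| 17 | 14 | 0.046 | 13/17, 0.126 | 13/16, 0.065 |
| 18 | 15 | 0.033 | 14/18, 0.094 | 14/17, 0.046 |
| 19 | 16 | 0.023 | 15/19, 0.070 | 15/18, 0.033 |
| 20 | 17 | 0.016 | 16/20, 0.051 | 16/19, 0.023 |
| 21 | 17 | 0.037 | 16/21, 0.096 | 16/20, 0.051 |
| 22 | 18 | 0.027 | 17/22, 0.072 | 17/21, 0.037 |
| 23 | 19 | 0.019 | 18/23, 0.054 | 18/22, 0.027 |
| 24 | 19 | 0.040 | 18/24, 0.096 | 18/23, 0.054 |

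With at least 16 kept, no removal works at n = 16 or 17, and one is enough at 18, 19, 20, 22 and 23. Two are needed at 21 (16/19, p = 0.023) and at 24 (18/22, p = 0.027). If the minimum is not enforced, one removal also reverses the result at n = 16.

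**Type I error under selective removal.** This model is an assumption, since the documents give no breach rate. Each non-responder independently has a removable breach with probability q. Up to two are removed when that produces p ≤ 0.05, at least 16 men remain, and no responder is ever removed. Let k(x) be the fewest removals that make x responders pass. Then

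type I error = Σ P(X = x | n, 0.60) × P(Bin(n − x, q) ≥ k(x)), summed over those x for which an allowed k(x) exists.

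At n = 18 only x = 14 is added, with four non-responders and one removal needed. P(X = 14) = 0.0614, so:

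- q = 5%: 0.0328 + 0.0614 × (1 − 0.95⁴) = 0.0442
- q = 10%: 0.0328 + 0.0614 × (1 − 0.90⁴) = 0.0539
- q = 20%: 0.0328 + 0.0614 × (1 − 0.80⁴) = 0.0690

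The same sum at every n:

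| q | 16 | 17 | 18 | 19 | 20 | 21 | 22 | 23 | 24 |
|---|---|---|---|---|---|---|---|---|---|
| 5% | 0.018 | 0.046 | 0.044 | 0.034 | 0.024 | 0.038 | 0.037 | 0.029 | 0.042 |
| 10% | 0.018 | 0.046 | 0.054 | 0.047 | 0.034 | 0.042 | 0.045 | 0.041 | 0.046 |
| 20% | 0.018 | 0.046 | 0.069 | 0.075 | 0.056 | 0.052 | 0.057 | 0.067 | 0.059 |

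**Benchmark.** If men are instead removed at random whatever their outcome (no cap, no minimum), type I error at n = 18 is 0.0353, 0.0318 and 0.0275 for q = 5%, 10% and 20%. At that n, the rise in the selective model therefore comes almost entirely from selection.

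**The case against.** The route is narrow. An exclusion criterion must actually have been breached, eligibility is checked before insertion (sections 8.7 and 9.2), and many criteria, such as fistula, bladder stones or dependence on an implant, are facts fixed before the device goes in. Discretion lies mostly in items such as comorbidities the investigator judges unsuitable. A breach calls for a deviation form (section 14.8.3), and enrollment criteria are among the items monitors may verify (section 15.1.1). All of this stands. It makes a removal visible, but it does not make the decision blind to results.

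The stakes are also modest. Section 10.2 concedes the point ("Although there will be limited power achieved with the number of patients completing this study") and presents the data as groundwork for later research. That lowers the importance, but the plan still keeps a hypothesis test at 0.05. The tipping point analyses in section 10.3 are open-ended and do not mention excluded men.

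Three stronger readings are tempting and are not supported:

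- **One removal can always decide the trial.** This fails at both counts the plan gives: at 16 if the minimum is kept, and at 24, where 18/23 still fails.
- **Section 14.2 already removes ineligible treated men.** It says "Only subjects who meet the inclusion/exclusion criteria, who signed the study enrollment informed consent will be considered enrolled in the study", while section 8 says all patients "that sign an informed consent form are considered to be part of the intended-to-treat (ITT) population". But section 14.2 sets an enrollment status and not an analysis set, the primary test uses neither term, and section 8.8 itself counts 36 enrolled men of whom only 24 are expected to be eligible. That mismatch is a separate editorial matter.
- **Serious safety events could be lost.** Section 10.3 already keeps serious adverse events from every treated man.

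**Conclusion.** The gap in the text is real. A treated man who is still being followed may be left out of the analysis on undefined grounds, by an unnamed person who may have seen his PVR values, and the set for the primary test is not defined. Confidence in that is high.

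The numerical consequence is fragility at some sample sizes. A reader might infer that the 5% level is inflated, but the documents give no breach rate and so do not show it. With the minimum of 16 kept and removal wholly selective, the level holds at 5% removability for every n from 16 to 24. At 10% it is exceeded only at n = 18. At 20%, meaning one non-responder in five with a usable breach, it is exceeded at every n from 18 to 24. This is a cheap improvement to the plan and not a fault that undermines it.

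**What to change.** Replace the first sentence of section 9.7.1.3 with:

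> Subjects later found to have met an exclusion criterion or failed an inclusion criterion remain in the primary efficacy analysis if they are in the mITT population, and in all safety analyses if treated. A sensitivity analysis excludes subjects who breached criteria listed in this protocol, judged only on facts that existed before first insertion, by someone without access to PVR data.

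List those criteria in the amendment itself. Naming them later would not be results-blind, because PVR is read at each device visit. The new sentence also repairs the inverted wording, under which failing to meet an exclusion criterion counts as the fault. In the second sentence, refer to this protocol in place of an arm, since the study has only one.

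Add to section 10.3:

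> mITT: all subjects who passed Device Tolerability Screening and have at least one PVR value with the device, regardless of eligibility breaches found later.

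The screening condition follows section 8.5.1. The PVR condition is new, added because responder status cannot be derived without a value.

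A pre-specified exclusion decided without sight of PVR would also close the gap. Retention is preferred because it leaves nothing to decide in the primary test.

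The cost is one rewritten paragraph, a short list of criteria, one definition and one sensitivity run, with no new data. The downside is that a truly ineligible man stays in the primary rate, with the sensitivity result reported beside it.
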